6.4. Appendix 4 Protocol Deviations

In general, the following list of major protocol deviations may have the potential to impact participants' rights, safety or well-being, or the integrity and/or result of the clinical study. Participants with major protocol deviations will be identified prior to database lock and the participants with major protocol deviations will be summarized by category. Details and definitions will be defined in the major protocol deviations criteria form (TV-FRM-04718).

- Missed Assessment/Visit
- Not Meeting the Inclusion or Meeting the Exclusion criteria
- Intake of Prohibited Concomitant Medication

Eligibility criteria deviations are deviations from Section 5.1 and 5.2 of the Protocol inclusion and exclusion criteria.

Post-entry deviations are deviations from the protocol that occurred after the patient was assigned to the study.

All major protocol deviation criteria will be listed by coded term and verbatim term.

Major PDs will be listed for patients with at least one corona virus disease 2019 (COVID-19) related PD, without any COVID-19 related PD being recorded and regardless of COVID-19 related PDs.

Additionally, listings for patients with major protocol deviations will be provided.

6.5. Appendix 5 Prior and Concomitant Medications

Prior and Concomitant medications will be coded using the World Health Organization Drug Dictionary (WHO-DD).

Prior medications are defined as any therapy used before the day of first dose (partial or complete) of study intervention. If the stop date is missing or partial and it cannot be determined whether the participant stopped the medication before the start of study intervention (guselkumab), the medication will be considered as concomitant.

Concomitant medications are defined as any therapy used on or after 12 weeks after last dose of guselkumab or 8 weeks if the patient switches to commercial guselkumab or any other drug, the same day as the first dose of study injection, including those that started before and continue on after the first dose of study intervention. If the start or stop date is missing or partial and cannot be determined, the medication will be considered as concomitant.

Summaries of concomitant medications will be presented by Anatomical Therapeutic Chemical (ATC) level terms (Level 2 and Level 4) and standardized medication name. The proportion of participants who receive each concomitant medication will be summarized as well as the proportion of participants who receive at least 1 concomitant medication. The proportion of participants receiving a medication will be summarized for Nicotine and Non-nicotine users and across the study (total). If participants receive a medication more than once within the treatment phase, they will be counted only once.

In addition, concomitant medications of special interest will be presented with at least $\geq 80\%$ of the total column. These include [special interest categories] and standardized medication name. See Appendix 9 for list of medications in each category.

Prior medications will be summarized by ATC term.

The concomitant medication data listing will be displayed on the Safety analysis set.

Percentages will be calculated relative to the number of participants in the Safety analysis set.

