#### 6.5.3. Concomitant Medications of Special Interest

Every effort should be made to keep participants on stable concomitant medications. If the medication is temporarily discontinued because of abnormal laboratory values, side-effects, concurrent illness, or the performance of a procedure, the change and reason for it should be clearly

documented in the participant's medical record. The Sponsor must be notified in advance (or as soon as possible thereafter) of any instances in which prohibited therapies are administered.

Details on permitted and prohibited concomitant medication relevant to the study is presented in Table 1. The medications detailed in the table are prohibited as they are known to affect CFR measurements or interact adversely with adenosine.

Table 1: Concomitant Medication of Special Interest

Drug class	Effect on CFR	Strength of evidence	Study rules
Products containing short- acting xanthine derivates eg, caffeine, etc. This includes beverages such as coffee, black/green tea, cola drinks	Decreases	Good	Allowed in the study but prohibited 12 hours before CFR procedure.
Drugs containing long- acting xanthine derivates eg, theophylline, diprophylline	Decreases	Good	Prohibited in study
Phenylephrine containing products	Increases	Good	Prohibited in study
NSAIDs*	Increases	Good	Allowed in stable dosing for at least 3 months before study. Prohibited are intermediate use >14 days and use on the day before and day of CFR measurement
ACEi	Increases	Good	Allowed in stable dosing for at least 3 months before study
ARBs	Losartan, no effect  Candesartan, increases	Moderate	Allowed in stable dosing for at least 3 months before study
Thiazide diuretics	No data available		Allowed in stable dosing for at least 3 months before study
Loop diuretics	No data available		Allowed in stable dosing for at least 3 months before study
Vitamin K antagonists	No data available		Prohibited in study
Platelet inhibitors (including ≤100mg ASA/d)	Increases	Good	Prohibited in study
Beta-blockers	First and second generation: Contradictory data Third generation: Increased	Good Moderate	Prohibited in study
Aldosterone blockers	Increases	Moderate	Prohibited in study
Calcium antagonists Sodium channel inhibitors (ranolazine)	Increases Increases	Good Moderate	Prohibited in study Prohibited in study
Statins	Increases (if therapy >8 weeks)	Good	Prohibited in study
Glucose lowering drugs	Insulin: Increases DPP4i: Mixed effects	Moderate Moderate	Prohibited in study

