5.3.2. Estimand

Primary Trial Objective: To evaluate the effect of guselkumab on CFR measured by transthoracic doppler-echocardiography, in participants with moderate-to-severe psoriasis and intermediate cardiovascular risk. Intermediate cardiovascular risk is defined by CFR ≥ 2 and ≤ 3.5 at Screening Visit S2.

Estimand Scientific Question of Interest: What level of change from baseline of CFR considered to have benefited from guselkumab for the pre-specified duration (32 weeks).

Study intervention:

• Guselkumab (100 mg SC [Subcutaneous] injections at Week 0, 4, 12, 20 and 28)

Population: Participants with moderate to severe plaque psoriasis (with or without PsA) for at least 6 months prior to study entry. The target population consists of men or women aged 18 years and above with moderate to severe plaque psoriasis of at least 6 months' duration, defined as psoriasis area and severity index (PASI) \geq 12, and involved body surface area (BSA) \geq 10% at Screening Visit S1 and CFR with \geq 2 to \leq 3.5 at Screening Visit S2. Participants should not be with CFR of \leq 2 or \geq 3.5 at both Screening Visit S2 and Week 0.

Variable: Change from baseline in the CFR measurement at Final Efficacy Visit (Week 32). The CFR measurement at Week 0, Baseline will be considered as baseline value. Participants who had adequate primary endpoint measurements will be assessed at Final Efficacy Visit (Week 32) considering as observed for the analysis.

Summary measure (Population-level summary): Least squares means (LSmeans), together with the 95% CI and p-values based on the MMRM.

Intercurrent events and their corresponding strategies:

Intercurrent Events	Strategy for Addressing Intercurrent Events and Its Description
	Composite Strategy: A participant with this intercurrent event will be excluded from the analysis.

^{*} List of concomitant medications from ADaM datasets will be shared with the clinical team after the receipt of SDTM data by the programming team for each data cut. The clinical team will review the list and flag the appropriate disallowed medications. This list will be used for the intercurrent events.

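### SAP 6.5 shows special-interest medications only at 80% use or more and turns the end of the concomitant window into a start; both sentences need rewriting (minor).

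*SAP*

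**What the plan says.** **Display rule.** SAP 6.5 (Appendix 5) first plans a summary of each concomitant medication by ATC level and drug name, by nicotine group and in total, with no threshold. It then adds that "concomitant medications of special interest will be presented with at least" 80% of the total column. It gives no reason for the threshold. Where the categories should be named there is an unfilled bracketed placeholder, and the reader is sent to Appendix 9 for the list. Appendix 9 (SAP 6.9) holds no list. It describes a spreadsheet from which the clinical team identifies disallowed and special-interest drugs.

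**Definition.** SAP 6.5 also states: "Concomitant medications are defined as any therapy used on or after 12 weeks after last dose of guselkumab or 8 weeks" if the participant switches to commercial guselkumab or another drug. The same sentence then runs on to the day of the first injection, "including those that started before and continue on after the first dose of study intervention". For unclear dates: "If the start or stop date is missing or partial and cannot be determined, the medication will be considered as concomitant".

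**Protocol.** Section 6.5 has concomitant therapy recorded from the first guselkumab dose until 12 weeks after the last. Section 6.5.3 explains why Table 1 exists: "The medications detailed in the table are prohibited as they are known to affect CFR measurements" or interact with adenosine. Despite that lead-in, the table's own study rules allow several classes under conditions, among them NSAIDs, ACE inhibitors, ARBs and diuretics.

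**The concern.** A special-interest table should show how many participants used drugs that can move the primary endpoint. A rule that shows only what at least four in five participants took works against that purpose, because such drugs are mostly prohibited or restricted. In a single-arm study there is no control group to absorb the effect of other CFR-active drugs, so a reader of the results would want this table.

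The definition matters because every concomitant-medication summary in SAP 6.5 depends on it. If 12 weeks after the last dose opens the window instead of closing it, the definition conflicts with the period over which the protocol collects the data.

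**Working it through.** **1. What 80% means as a count.** Users needed = 0.80 × N, rounded up. The planned N of 50 is in SAP 3. The final N is not given; SAP Appendix 2 says only that it was low. The percentages use the Safety Analysis Set, whose size is also not given. The smaller N and the usage rates p below are therefore assumptions, chosen to show a range. The last two columns give P(X ≥ users needed) with X ~ Binomial(N, p).

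| N | Users needed | p = 0.30 | p = 0.50 |
|---|---|---|---|
| 50 (planned) | 0.80 × 50 = 40 | 3.9 × 10⁻¹³ | 1.2 × 10⁻⁵ |
| 20 (assumed) | 0.80 × 20 = 16 | 5.6 × 10⁻⁶ | 0.006 |
| 10 (assumed) | 0.80 × 10 = 8 | 0.0016 | 0.055 |

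Even a drug that half of such participants would be expected to take has about a 5% chance of being displayed at N = 10, and far less at larger N. One row of Protocol Table 1 could be an exception: caffeine-containing products are allowed apart from the 12 hours before the CFR procedure. They could reach 80% if they were recorded as concomitant therapy at all. The table is therefore almost certainly empty of the drugs of concern, but not empty by necessity.

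**2. What remains without that table.**
- SAP 6.5: an unthresholded summary by ATC level and drug name, and a listing on the Safety Analysis Set.
- SAP 5.3.2 and 6.9: review and flagging by the clinical team at each data cut. Section 5.3.2 covers disallowed drugs; 6.9 covers disallowed and special-interest drugs.
- SAP 6.4: taking prohibited medication is a major deviation category, summarized and listed.

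The outputs in 5.3.2 and 6.4 concern disallowed or prohibited drugs. For permitted classes that Table 1 rates as raising CFR with good evidence (NSAIDs, ACE inhibitors), the flag in 6.9 feeds no named summary other than the one filtered at 80%.

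**3. The window, side by side.**
- Protocol 6.5: opens at the first dose, closes 12 weeks after the last dose.
- SAP 6.5, first clause: opens 12 weeks after the last dose (8 on switching), with no stated close.
- Timing: the last planned dose is at Week 28. 28 + 12 = Week 40 and 28 + 8 = Week 36, which are the protocol's two Final Safety Visit times. Both figures fit the end of a window.

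**4. The literal gap.** Take a drug started at Week 4 (Day 29 in SAP Table 2) and stopped at Week 12 (Day 85). It was not used before the first dose, so it is not prior. It was not used on the day of the first dose, nor carried across it. It was not used at or after 12 weeks past the last dose (Day 197 + 84 = Day 281), or at or after 8 weeks (Day 197 + 56 = Day 253). So it is not concomitant either. The default for missing dates does not help, because both dates are known.

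**The case against.** The strongest reply is that little is actually lost. The 80% rule governs an additional display only, and a drug taken by a single participant would still appear in the ATC summary and the listing. This stands. A reader might infer that CFR-affecting drugs would go unshown or unflagged; the outputs in SAP 5.3.2, 6.4, 6.5 and 6.9 rule that out.

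A reader might also infer that the filter changes who is excluded from the primary analysis, because SAP 5.3.2 says of its flagged medication list: "This list will be used for the intercurrent events". That list comes from clinical review of the concomitant-medication data, not from the filtered table, so the 80% rule cannot affect it. The SAP does not say whether the reviewed list is restricted by the 6.5 definition, which is one more reason to have the definition unambiguous.

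On the definition, the intended meaning can be recovered. The sentence goes on to the day of the first dose and to continuing therapies, and the section counts repeat use once within the treatment phase. The documents therefore do not support reading it as a deliberate rule that concomitant use begins only after follow-up. It is scrambled wording.

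Two further points limit the weight. ACE inhibitors, ARBs and diuretics are allowed only if stable for at least 3 months before the study, so they should already act at baseline and explain less of a change. And mock-ups and programming instructions sit in a separate specification document that may handle the threshold differently. The approved SAP text is still what a programmer would follow.

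**Conclusion.** The point holds as a minor one. Two rules in SAP 6.5 are wrong as written. The 80% condition leaves the special-interest table almost certainly empty (40 of 50 users needed at the planned N) and removes the only summary by special-interest category for permitted CFR-active drugs. The definition contradicts Protocol 6.5 on which end of the window 12 weeks marks and, taken literally, leaves drugs started and stopped on treatment unclassified.

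The first conclusion assumes that the percentage is applied to the Safety Analysis Set total and that use of CFR-active drugs is well below 80%, as the protocol's restrictions imply. The second depends only on the wording. Neither shows that a drug would be missing from every output, or that the primary analysis population changes.

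**What to change.** 1. Delete the 80% condition and show every special-interest category with any use, by nicotine group and in total.
2. Replace the bracketed placeholder, and fill Appendix 9, with the drug classes of Protocol Table 1.
3. Define concomitant therapy as any therapy used at any time from the day of the first guselkumab dose through 12 weeks after the last dose, or 8 weeks if the participant switches, including therapies begun earlier and still continuing. Protocol 6.5 gives only the 12-week limit, so the 8-week variant should be noted in SAP Appendix 2.
4. State in SAP 5.3.2 whether the list reviewed for intercurrent events uses this definition.

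The cost is a few SAP sentences and a slightly longer table. No new data are needed.

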6.6. Appendix 6 Medical History

Investigators should document all significant medical conditions that the participant has experienced in the past. Any medical condition present at the time informed consent is given is to be regarded as concomitant. A condition first occurring or detected on or after the day of the Baseline visit and/or worsening of a concomitant condition on or after the day of the baseline visit is to be documented as an AE on the CRF.

All conditions will be coded using latest version of MedDRA.

- A summary of medical history will be provided.
- A listing of medical history will be provided.

6.7. Appendix 7 Intervention Compliance

All guselkumab discontinuations, and the primary reasons for the discontinuation will be recorded in the Electronic case report form (eCRF).

Compliance to guselkumab will be summarized up to Week 28 only.

Compliance will be summarized descriptively.

The number and percentage of participants who have at least 80% compliance through the time of visit will be summarized.

Compliance will be calculated as follows:

Compliance (%) = 100 x Completed injections/total possible injections

Compliance will be summarized by Nicotine use, non-Nicotine use and Total group, descriptive statistics will be provided with N, mean, SD, median, and range (minimum, maximum). In addition, the number (%) of participants in each compliance categories will be presented.

6.8. Appendix 8 Adverse Events of Special Interest

Adverse events of special interest are categorized preferred terms. Adverse events of special interest will be programmatically derived from a predefined list of preferred terms (as mentioned in section 8.3.6 of the study protocol) from an external data from the clinical team.

6.9. Appendix 9 Medications of Special Interest

A listing of concomitant medications (excel file) will be provided by the ClinChoice programming team with treatment start date, study day, and duration to the sponsor clinical team to identify the disallowed medication and medication of special interest in the study. During the study the spreadsheet will be updated for every data cut and the list with flagging will be updated accordingly.

6.10. Appendix 10 Laboratory Toxicity Grading

The grading scale use for lab assessments is based on 'Common Terminology Criteria for Adverse Events (CTCAE) v5.0'.

If a laboratory value falls within the grading as specified below but also within the local laboratory normal limits, the value is considered to be normal and will be reset to grade 0.

Pre-baseline measurements will use the same grading ranges as applied to baseline measurements. In case a test has two sets of ranges — one for baseline normal and one for baseline abnormal, the one for baseline normal will be applied for all measurements taken pre-baseline and on baseline.

CTCAE Term	Grade 1	Grade 2	Grade 3	Grade 4	Janssen implementation notes
Blood and lymphatic syst	em disorders				
Anemia	Hemoglobin (Hgb) <lln -="" 10.0="" 100="" 6.2="" <lln="" dl;="" g="" l;="" l<="" mmol="" td="">Hemoglobin (Hgb) <10.0 - 8.0 g/dL; <6.2 - 4.9 mmol/L; <100 - 80g/L	Hemoglobin (Hgb) <8.0 g/dL; <4.9 mmol/L; <80 g/L; transfusion indicated	Life-threatening consequences; urgent intervention indicated	Clinical signs and symptoms are not taken into consideration for grading.	</lln>	Hemoglobin (Hgb) <10.0 - 8.0 g/dL; <6.2 - 4.9 mmol/L; <100 - 80g/L	Hemoglobin (Hgb) <8.0 g/dL; <4.9 mmol/L; <80 g/L; transfusion indicated	Life-threatening consequences; urgent intervention indicated	Clinical signs and symptoms are not taken into consideration for grading.
Leukocytosis	-	-	>100,000/mm3; >100 x 10e9 /L	Clinical manifestations of leucostasis; urgent intervention indicated	Clinical signs and symptoms are not taken into consideration for grading; Added ranges in SI unit (x 10e9 /L)
Investigations			•		
Alanine aminotransferase increased	>ULN - 3.0 x ULN if baseline was normal; 1.5 - 3.0 x baseline if baseline was abnormal	>3.0 - 5.0 x ULN if baseline was normal; >3.0 - 5.0 x baseline if baseline was abnormal	>5.0 - 20.0 x ULN if baseline was normal; >5.0 - 20.0 x baseline if baseline was abnormal	>20.0 x ULN if baseline was normal; >20.0 x baseline if baseline was abnormal	Ranges defined for "abnormal baseline" are applied only if baseline > ULN. If baseline < LLN, then ranges for "normal baseline" are applied.
Alkaline phosphatase increased	>ULN - 2.5 x ULN if baseline was normal; 2.0 - 2.5 x baseline if baseline was abnormal	>2.5 - 5.0 x ULN if baseline was normal; >2.5 - 5.0 x baseline if baseline was abnormal	>5.0 - 20.0 x ULN if baseline was normal; >5.0 - 20.0 x baseline if baseline was abnormal	>20.0 x ULN if baseline was normal; >20.0 x baseline if baseline was abnormal	Ranges defined for "abnormal baseline" are applied only if baseline > ULN. If baseline < LLN, then ranges for "normal baseline" are applied.
Aspartate aminotransferase increased	>ULN - 3.0 x ULN if baseline was normal; 1.5 - 3.0 x baseline if baseline was abnormal	>3.0 - 5.0 x ULN if baseline was normal; >3.0 - 5.0 x baseline if baseline was abnormal	>5.0 - 20.0 x ULN if baseline was normal; >5.0 - 20.0 x baseline if baseline was abnormal	>20.0 x ULN if baseline was normal; >20.0 x baseline if baseline was abnormal	Ranges defined for "abnormal baseline" are applied only if baseline > ULN. If baseline < LLN, then ranges for "normal baseline" are applied.
Blood bilirubin increased	>ULN - 1.5 x ULN if baseline was normal; > 1.0 - 1.5 x baseline if baseline was abnormal	>1.5 - 3.0 x ULN if baseline was normal; >1.5 - 3.0 x baseline if baseline was abnormal	>3.0 - 10.0 x ULN if baseline was normal; >3.0 - 10.0 x baseline if baseline was abnormal	>10.0 x ULN if baseline was normal; >10.0 x baseline if baseline was abnormal	Ranges defined for "abnormal baseline" are applied only if baseline > ULN. If baseline < LLN, then ranges for "normal baseline" are applied.

CONFIDENTIAL – FOIA Exemptions Apply in U.S. Status: Approved, Date: 21 July 2023

CTCAE Term	Grade 1	Grade 2	Grade 3	Grade 4	Janssen implementation notes
Cholesterol high	>ULN - 300 mg/dL;	>300 - 400 mg/dL;	>400 - 500 mg/dL;	>500 mg/dL;	•
	>ULN - 7.75 mmol/L	>7.75 - 10.34 mmol/L	>10.34 - 12.92 mmol/L	>12.92 mmol/L	
CPK increased	>ULN - 2.5 x ULN	>2.5 x ULN - 5 x ULN	>5 x ULN - 10 x ULN	>10 x ULN	
Creatinine increased	Creatine Kinase	Creatine Kinase	Creatine Kinase	Creatine Kinase	
	>ULN - 1.5 x ULN	>1.5 - 3.0 x baseline;	>3.0 x baseline;	>6.0 x ULN	
		>1.5 - 3.0 x ULN	>3.0 - 6.0 x ULN		
GGT increased	>ULN - 2.5 x ULN if	>2.5 - 5.0 x ULN if	>5.0 - 20.0 x ULN if	>20.0 x ULN if baseline	Ranges defined for
	baseline was normal;	baseline was normal;	baseline was normal;	was normal;	"abnormal baseline" are
	2.0 - 2.5 x baseline if	>2.5 - 5.0 x baseline if	>5.0 - 20.0 x baseline if	>20.0 x baseline if	applied only if baseline >
	baseline was abnormal	baseline was abnormal	baseline was abnormal	baseline was abnormal	ULN. If baseline < LLN,
					then ranges for "normal
					baseline" are applied.
Hemoglobin increased	Increase in >0 - 2 g/dL;	Increase in $>$ 2 - 4 g/dL;	Increase in >4 g/dL;	-	The increase indicates
	Increase in >0 - 20 g/L	Increase in >20 - 40 g/L	Increase in >40 g/L		the level of increase
					above normal (above
					ULN). Applied as, e.g.,
					grade 1 (g/dL): >ULN –
					ULN+2 g/dL;
					Added ranges in SI unit
					(g/L).
INR increased	>1.2 - 1.5;	>1.5 - 2.5;	>2.5;	-	Concomitant therapy or
	>1 - 1.5 x baseline if on	>1.5 - 2.5 x baseline if	>2.5 x baseline if on		clinical signs and
	anticoagulation;	on anticoagulation;	anticoagulation;		symptoms are not taken
	monitoring only	dose adjustment	bleeding		into consideration for
T 1	indicated	indicated 2	.500 200/ 2	200/ 2	grading.
Lymphocyte count	<lln -="" 800="" mm3;<="" td=""><800 - 500/mm3;	<500 - 200/mm3;	<200/mm3;		</lln>	<800 - 500/mm3;	<500 - 200/mm3;	<200/mm3;	
decreased	<lln -="" 0.8="" 10e9="" l<="" td="" x=""><0.8 - 0.5 x 10e9 /L	<0.5 - 0.2 x 10e9 /L	<0.2 x 10e9 /L	4 11 1 CT	</lln>	<0.8 - 0.5 x 10e9 /L	<0.5 - 0.2 x 10e9 /L	<0.2 x 10e9 /L	4 11 1 CT
Lymphocyte count	-	>4000/mm3 -	>20,000/mm3;	-	Added ranges in SI unit
increased		20,000/mm3;	>20 x 10e9 /L		(x 10e9 /L).
NT 121	J. J. 1500/ 2	>4 - 20 x 10e9 /L	.1000 700/ 2	.500/ 2	D 131 . 131 1
Neutrophil count	<lln -="" 1500="" mm3;<="" td=""><1500 - 1000/mm3;	<1000 - 500/mm3;	<500/mm3;	Both Neutrophils and	</lln>	<1500 - 1000/mm3;	<1000 - 500/mm3;	<500/mm3;	Both Neutrophils and
decreased	<lln -="" 1.5="" 10e9="" l<="" td="" x=""><1.5 - 1.0 x 10e9 /L	<1.0 - 0.5 x 10e9 /L	<0.5 x 10e9 /L	segmented neutrophils	</lln>	<1.5 - 1.0 x 10e9 /L	<1.0 - 0.5 x 10e9 /L	<0.5 x 10e9 /L	segmented neutrophils
					are graded using these
Platelet count decreased	ZIIN 75 000/2	<75.000 50.000/2	<50.000 25.000/2	<25,000/mm3;	criteria.
rialeiel count decreased	<lln -="" 75,000="" mm3;<="" td=""><75,000 - 50,000/mm3;	<50,000 - 25,000/mm3;			</lln>	<75,000 - 50,000/mm3;	<50,000 - 25,000/mm3;		
White blood cell	<lln -="" 10e9="" 75.0="" l<="" td="" x=""><75.0 - 50.0 x 10e9 /L	<50.0 - 25.0 x 10e9 /L	<25.0 x 10e9 /L		</lln>	<75.0 - 50.0 x 10e9 /L	<50.0 - 25.0 x 10e9 /L	<25.0 x 10e9 /L	
	<lln -="" 3000="" mm3;<="" td=""><3000 - 2000/mm3; <3.0	<2000 - 1000/mm3; <2.0	<1000/mm3;		</lln>	<3000 - 2000/mm3; <3.0	<2000 - 1000/mm3; <2.0	<1000/mm3;	
decreased	<lln -="" 10e9="" 3.0="" l<="" td="" x="">- 2.0 x 10e9 /L	- 1.0 x 10e9 /L	<1.0 x 10e9 /L		</lln>	- 2.0 x 10e9 /L	- 1.0 x 10e9 /L	<1.0 x 10e9 /L	

CTCAE Term	Grade 1	Grade 2	Grade 3	Grade 4	Janssen implementation notes
Metabolism and nutriti	ion disorders				•
Acidosis	pH <normal, but="">=7.3</normal,>	-	pH <7.3	Life-threatening consequences	pH <normal is
implemented as pH <lln. Clinical signs and symptoms are not taken into consideration for grading.</lln. </normal>
Alkalosis	pH >normal, but <=7.5	-	pH >7.5	Life-threatening consequences	pH >normal is implemented as pH >ULN. Clinical signs and symptoms are not taken into consideration for grading.
Hyperkalemia	Potassium >ULN - 5.5 mmol/L	Potassium >5.5 - 6.0 mmol/L; intervention initiated	Potassium >6.0 - 7.0 mmol/L; hospitalization indicated	Potassium >7.0 mmol/L; life-threatening consequences	Clinical signs and symptoms are not taken into consideration for grading.
Hypermagnesemia	Magnesium >ULN - 3.0 mg/dL; >ULN - 1.23 mmol/L	-	Magnesium >3.0 - 8.0 mg/dL; >1.23 - 3.30 mmol/L	Magnesium >8.0 mg/dL; >3.30 mmol/L; life-threatening consequences	Clinical signs and symptoms are not taken into consideration for grading.
Hypernatremia	Sodium >ULN - 150 mmol/L	Sodium >150 - 155 mmol/L; intervention initiated	Sodium >155 - 160 mmol/L; hospitalization indicated	Sodium >160 mmol/L; life-threatening consequences	Clinical signs and symptoms are not taken into consideration for grading.
Hypertriglyceridemia	Triglycerides 150 mg/dL - 300 mg/dL; 1.71 mmol/L - 3.42 mmol/L	Triglycerides >300 mg/dL - 500 mg/dL; >3.42 mmol/L - 5.7 mmol/L	Triglycerides >500 mg/dL - 1000 mg/dL; >5.7 mmol/L - 11.4 mmol/L	Triglycerides >1000 mg/dL; >11.4 mmol/L; life-threatening consequences	Clinical signs and symptoms are not taken into consideration for grading.
Hypoalbuminemia	Albumin <lln -="" 3="" dl;
<lln -="" 30="" g="" l<="" td="">Albumin <3 - 2 g/dL; <30 - 20 g/L	Albumin <2 g/dL; <20 g/L	Life-threatening consequences; urgent intervention indicated	Clinical signs and symptoms are not taken into consideration for grading.	</lln></lln>	Albumin <3 - 2 g/dL; <30 - 20 g/L	Albumin <2 g/dL; <20 g/L	Life-threatening consequences; urgent intervention indicated	Clinical signs and symptoms are not taken into consideration for grading.

 $CONFIDENTIAL-FOIA\ Exemptions\ Apply\ in\ U.S.$

CTCAE Term	Grade 1	Grade 2	Grade 3	Grade 4	Janssen implementation notes
Hypocalcemia	Corrected serum calcium of <lln -="" 2.0="" 8.0="" <lln="" dl;="" l;<="" mg="" mmol="" td="">Corrected serum calcium of <8.0 - 7.0 mg/dL; <2.0 - 1.75 mmol/L; Ionized calcium <1.0 -	Corrected serum calcium of <7.0 - 6.0 mg/dL; <1.75 - 1.5 mmol/L; Ionized calcium <0.9 -	Corrected serum calcium of <6.0 mg/dL; <1.5 mmol/L; Ionized calcium <0.8	Clinical signs and symptoms are not taken into consideration for grading.	</lln>	Corrected serum calcium of <8.0 - 7.0 mg/dL; <2.0 - 1.75 mmol/L; Ionized calcium <1.0 -	Corrected serum calcium of <7.0 - 6.0 mg/dL; <1.75 - 1.5 mmol/L; Ionized calcium <0.9 -	Corrected serum calcium of <6.0 mg/dL; <1.5 mmol/L; Ionized calcium <0.8	Clinical signs and symptoms are not taken into consideration for grading.
	1.0 mmol/L	0.9 mmol/L; symptomatic	0.8 mmol/L; hospitalization indicated	mmol/L; life-threatening consequences	
Hypoglycemia	Glucose <lln -="" 55="" dl;
<lln -="" 3.0="" l<="" mmol="" td="">Glucose <55 - 40 mg/dL; <3.0 - 2.2 mmol/L	Glucose <40 - 30 mg/dL; <2.2 - 1.7 mmol/L	Glucose <30 mg/dL; <1.7 mmol/L; life-threatening consequences; seizures	Clinical signs and symptoms are not taken into consideration for grading. Urine glucose is not graded.	</lln></lln>	Glucose <55 - 40 mg/dL; <3.0 - 2.2 mmol/L	Glucose <40 - 30 mg/dL; <2.2 - 1.7 mmol/L	Glucose <30 mg/dL; <1.7 mmol/L; life-threatening consequences; seizures	Clinical signs and symptoms are not taken into consideration for grading. Urine glucose is not graded.
Hypokalemia	Potassium <lln -="" 3.0
mmol/L</lln>	Symptomatic with Potassium <lln -="" 3.0="" indicated<="" intervention="" l;="" mmol="" td="">Potassium <3.0 - 2.5 mmol/L; hospitalization indicated	Potassium <2.5 mmol/L; life-threatening consequences	"Symptomatic" ranges are applied for grade 2, grade 1 not assigned, i.e., worst case applied. Clinical signs and symptoms are not taken into consideration for grading of grade 3 and 4.	</lln>	Potassium <3.0 - 2.5 mmol/L; hospitalization indicated	Potassium <2.5 mmol/L; life-threatening consequences	"Symptomatic" ranges are applied for grade 2, grade 1 not assigned, i.e., worst case applied. Clinical signs and symptoms are not taken into consideration for grading of grade 3 and 4.
Hypomagnesemia	Magnesium <lln -="" 0.5="" 1.2="" <lln="" dl;="" l<="" mg="" mmol="" td="">Magnesium <1.2 - 0.9 mg/dL; <0.5 - 0.4 mmol/L	Magnesium <0.9 - 0.7 mg/dL; <0.4 - 0.3 mmol/L	Magnesium <0.7 mg/dL; <0.3 mmol/L; life-threatening consequences	Clinical signs and symptoms are not taken into consideration for grading.	</lln>	Magnesium <1.2 - 0.9 mg/dL; <0.5 - 0.4 mmol/L	Magnesium <0.9 - 0.7 mg/dL; <0.4 - 0.3 mmol/L	Magnesium <0.7 mg/dL; <0.3 mmol/L; life-threatening consequences	Clinical signs and symptoms are not taken into consideration for grading.
Hyponatremia	Sodium <lln -="" 130
mmol/L</lln>	Sodium 125-129 mmol/L and asymptomatic	Sodium 125-129 mmol/L symptomatic; 120-124 mmol/L regardless of symptoms Sodium <130-120 mmol/L	Sodium <120 mmol/L; life-threatening consequences	Clinical signs and symptoms are not taken into consideration for grading. Worst case ("<130-120 mmol/L" for grade 3 added by Janssen) is applied across grade 2/3 ranges: 120-129 mol/L

CTCAE Term	Grade 1	Grade 2	Grade 3	Grade 4	Janssen implementation notes
					assigned to grade 3, grade 2 not used.
Renal and urinary disord	lers				
Proteinuria	1+ proteinuria; urinary protein ≥ULN - <1.0 g/24 hrs; urinary protein ≥ULN - <1000 mg/day	Adult: 2+ and 3+ proteinuria; urinary protein 1.0 - <3.5 g/24 hrs; urinary protein 1000 - <3500 mg/day Pediatric: Urine P/C (Protein/Creatinine) ratio 0.5 - 1.9; Urine P/C (Protein/Creatinine) 56.5 - 214.7 g/mol	Adult: 4+ proteinuria; urinary protein >=3.5 g/24 hrs; urinary protein >=3500 mg/day; Pediatric: Urine P/C (Protein/Creatinine) ratio >1.9; Urine P/C (Protein/Creatinine) >214.7 g/mol	-	In case both 24-h urine collection and dipstick are collected, then worst case is taken, as opposed to having 24-h urine collection take precedence over dipstick. Added ranges in SI unit for urinary protein (mg/day) and for urine P/C (g/mol). Pediatric grading is applied to age range [0-18]. Adult grading is applied for ages [>18].

^{*} Grade 0 is assigned to a lab assessment when the lab test is described in the table, but the lab value is not assigned a grade 1 or higher.

6.11. Appendix 11 Potential Risks due to Study Procedure (Adenosine Injection).

Potential Risks due to Study Procedure (Adenosine Injection)				
	Indications for Stopping Adenosine Infusion and/or Administering			
Potential Risks of Clinical Significance	Aminophylline	Mitigation Strategy		
Vascular related: Flushing	Stopping Adenosine and/or further medical intervention is at the discretion of the cardiology investigator and should be considered in case of:	The half-life of adenosine is less than 10 seconds. Thus, the adverse effects are generally rapidly self-limiting. Treatment of any Prolonged adverse effect should be individualized and directed toward the specific effect.		
Thoracic related: dyspnea (shortness of breath), chest discomfort	Severe hypotension: Systolic pressure <80 mm Hg or 20 mmHg fall which persists	Stop infusion –most effects resolve within 30- 60 seconds post infusion		
Nervous system related: Headache, dizziness, lightheadedness, paresthesia	• ST depression: >3 mm beyond baseline ECG without angina or >2 mm with angina	• If symptoms persist, administer aminophylline, 125 mg, IV by slow infusion (1 minute) on cardiology investigator's direction. Dosage may be repeated in five minutes if there is no response to the first dose.		
Gastrointestinal related: Nausea	Persistent 2nd or 3rd degree heart block	Note: Adverse events (AEs) should be reported if medical intervention beyond stopping adenosine infusion is necessary. Please refer Appendix 13 of protocol for further information.		
• Cardiac related: bradycardia, sinus pause, skipped beats, atrial extrasystoles, Atrio- Ventricular block, ventricular excitability disorders such as ventricular extrasystoles, non-sustained ventricular tachycardia	Severe chest discomfort, dizziness, dyspnea, headache, nausea, syncope or dysrhythmia			

CONFIDENTIAL – FOIA Exemptions Apply in U.S. Status: Approved, Date: 21 July 2023

